## 6. Patients safety

Administration of the IPC device is a part of standard clinical practice, so patients will be not exposed to additional risk. The most common complication for ECS and IPC is a skin lesion on the legs. However, patients will be monitored for the possibility of developing any of the following: leg skin injury related to mechanical prophylaxis, ischemic changes in the lower limbs, and patient discomfort. There is no reason to expect the incidence would exceed what is encountered in daily practice.

## 7. Ethical issues

The study Protocol and all Amendments should be approved by Ethical Committee of the Pirogov Russian National Research Medical University. All subjects must be enrolled in the study after reading the patient's information sheet and providing informed consent. All participants will be able to withdraw their consent and stop participation at any time.

## 8. Statistical analysis plan and sample size calculation

**Statistical analysis plan.** The primary statistical analysis is designed as intention-to-treat with the use of two-tailed Fisher's exact test to compare the primary endpoint between two groups. The primary endpoint will be reported as an absolute number, percentage, and relative risk with 95% CI. Secondary statistical analysis of the primary endpoint will be made using an unadjusted Cox proportional-hazards model. The data will be censored on the time of VTE registration, or death, or discharge from the hospital and reported as a hazard ration with 95% CI. Kaplan-Meier curves will be used to compare time-to-event distribution. Cox proportional-hazards models adjusted for the clinical center, surgery profile, type of surgery, emergency of surgery, type of anesthesia, surgical radicalism, malignant disorder, Caprini score, and time to start LMWH injections will be used.

A similar analysis for the per-protocol population, but that excluded patients with gross violations of the protocol and premature discontinuation of at least one component of combined prophylaxis (ECS, IPC or LMWH), will be performed for the primary endpoint.

Secondary endpoints will be analyzed with two-tailed Fisher's exact test and will be represented as an absolute number, percentage, and relative risk with 95% CI.

Cox proportional-hazards models will be used for the prespecified subgroup analysis for the following subgroups: surgical profile; type of surgery; the urgency of surgery; the radicalism of surgery; type of anesthesia; malignant or benign disorder; preoperative, postoperative, or delayed start of LMWH injections; and pre-operative or post-operative IPC application.

Sensitivity analysis will address to the per-protocol analysis, compliance with IPC (restricted for 90% and more), duration of follow-up (restricted to 7 days and more), and the number of postoperative DUS (restricted with two and more).

Missing data on the primary endpoint are not anticipated in the inpatient settings, so no analysis for missing data being planned.

Adjusting for multiple comparisons and imputation for missing values will not be performed. The 95% confidence intervals will be not adjusted for multiplicity, and therefore, inferences drawn from these intervals might be not reproducible. The interim analysis is not planned.

**Sample size calculation.** The prevalence of asymptomatic postoperative vein thrombosis at the top of standard prophylaxis with ECS and LMWH was assumed as 30% based on our previous observations involving patients at high and extremely high risk. Taking into account the fact that pharmaco-mechanical prophylaxis should provide a further 60% VTE risk reduction, the absolute difference of 18% is assumed. Using Fisher's exact test for primary statistic analysis, with a power of 80% and type I error of 0.05, the sample size is estimated as 180 subjects (90+90 in each group). Assuming 10% withdrawal due to the protocol deviations, patient's decision, or incomplete data, the sample size is calculated as 200 subjects. Considering prespecified subgroup analysis for the patients with an early and delayed start of LMWH, we decided to double the sample size to achieve sufficient power for separate analyses of the suggested subgroups. IBM SPSS will be used for data processing.

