### **3.5. Endpoints and definitions**

**Primary endpoint:** asymptomatic venous thrombosis of the lower limbs detected by DUS during inpatient treatment.

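### The Cox/Kaplan-Meier rule lists VTE as a censoring time and leaves the event undefined; with death and discharge censored, 1 minus Kaplan-Meier does not estimate inpatient incidence

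*Combined protocol and SAP*

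**What the plan says.** Section 3.5 defines the primary endpoint as "asymptomatic venous thrombosis of the lower limbs detected by DUS during inpatient treatment". Section 8 compares it by intention to treat with a "two-tailed Fisher's exact test to compare the primary endpoint between two groups", reporting number, percentage and relative risk.

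A time-to-event analysis follows: "Secondary statistical analysis of the primary endpoint will be made using an unadjusted Cox proportional-hazards model". Its only rule on follow-up is "The data will be censored on the time of VTE registration, or death, or discharge from the hospital", and the result is to be given as a hazard ratio with a 95% CI. Then: "Kaplan-Meier curves will be used to compare time-to-event distribution". Cox models are also planned for covariate adjustment and for the prespecified subgroups.

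No sentence states what the event is in these models, and no competing-risk method is named. Section 3.3 uses VTE more widely than the primary endpoint: any VTE that is a primary or secondary endpoint leads to withdrawal. Section 3.5 lists symptomatic PE, fatal PE and total VTE as inpatient secondary endpoints.

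**The concern.** There are two separate problems.

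**The event is not defined.** VTE registration appears beside death and discharge as a censoring time. Even if this is loose wording for the end of follow-up, two readings remain. If the event is asymptomatic thrombosis only, a patient whose first VTE is symptomatic is censored. If the event is any VTE, the model no longer analyses the primary endpoint, although section 8 says that it does. The choice can change the event count and the hazard ratio. In an open-label trial it should be fixed before the data are seen.

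**Death and discharge are handled as ordinary censoring.** Kaplan-Meier treats a discharged or dead patient as someone who could still have had the event later. For an endpoint confined to the hospital stay, that cannot happen. The complement of the curve then answers a different question from the inpatient percentage, and one report could carry two visibly different figures for what looks like the same endpoint.

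**Working it through.** **The plan's own figure.** The plan gives no figure for the Cox/Kaplan-Meier analysis. Its rates come from the sample size paragraph: the control rate "was assumed as 30% based on our previous observations", and "the absolute difference of 18% is assumed", so 30% against 12%. For these rates, two-sided 0.05 and 80% power, the two-proportion formula with continuity correction gives 90 per arm, or 180 in total, as stated. Exact Fisher power at 90 per arm is 81.2%, and 180/0.9 = 200. The point below does not touch these numbers.

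**Inputs for the check**
- Inpatient incidence 30% (control) and 12% (IPC): section 8.
- Stay: section 4.2 gives only a minimum of 7 days of LMWH up to discharge. Uniform from 7 to 21 days is an assumption.
- Shape of the thrombosis hazard: not given, so three shapes are assumed.
- No deaths, and stay independent of thrombosis: assumptions that keep the check simple.

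**Formulas.** Let S(t) be the probability of no thrombosis by day t if nobody were discharged. Kaplan-Meier with discharge censored estimates S(t), so its complement at day 21 is 1 − S(21). The inpatient incidence is the chance that thrombosis comes before discharge:

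P = 1 − (1/14) ∫ S(u) du, for u from 7 to 21.

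**Constant hazard λ.** Here P = 1 − [exp(−7λ) − exp(−21λ)] / (14λ).
- Control: P = 0.30 gives λ = 0.02587 per day. Check: (0.8344 − 0.5809)/0.3621 = 0.700. Then 1 − S(21) = 1 − 0.5809 = 41.9%.
- IPC: P = 0.12 gives λ = 0.00918 per day. Check: (0.9378 − 0.8247)/0.1285 = 0.880. Then 1 − S(21) = 1 − 0.8247 = 17.5%.

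**Decaying hazard a·exp(−t/5).** The cumulative hazard is 5a[1 − exp(−t/5)].
- Control: a = 0.0778, so 1 − S(21) = 31.8%.
- IPC: a = 0.0279, so 1 − S(21) = 12.8%.

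**All events by day 7.** Nobody has been discharged when the events occur, so both estimators give 30% and 12%.

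| Assumed hazard | Inpatient incidence, control / IPC | 1 − KM at day 21, control / IPC | Excess, control |
|---|---|---|---|
| All events by day 7 | 30% / 12% | 30% / 12% | 0 points |
| Decaying | 30% / 12% | 31.8% / 12.8% | 1.8 points |
| Constant | 30% / 12% | 41.9% / 17.5% | 11.9 points |

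The excess also depends on the day. With constant hazard, the control arm shows none at day 7 (16.6% on both) and 3.4 points at day 14 (30.4% against 27.0%).

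The difference between arms at day 21 under constant hazard is 41.9 − 17.5 = 24.4 points, against 18 in the plan. The ratio hardly moves: 17.5/41.9 = 0.42 against 12/30 = 0.40.

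**Other stays.** The 12 points are not a ceiling. A simulation with constant hazard, log-normal stays (median 10 days, minimum 3) and a death hazard equal to 10% by day 10 gave, for control, 40.0% against 28.8% at day 14. At day 21 it gave 53.6% against 29.9%, with about 2 of 200 patients still at risk.

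**The case against.** The case against has real weight.

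- **The literal reading is not credible.** A reader might infer that the analysis would contain no events, out of about 84 expected in the doubled sample (200 × 0.30 + 200 × 0.12). The same sentence promises a hazard ratio, and the one before it names the primary endpoint, so the intended meaning is surely that follow-up stops at these times. This stands: the wording must be corrected, but it does not show that the analysis would be run without events.
- **The inpatient percentage is already estimated directly** by the primary analysis, and the plan says only that the curves compare distributions. This stands, and it limits the harm to how the curves will be read.
- **Cox models survive.** A reader might infer that the adjusted and subgroup results are biased as well. Once the event is defined, a Cox model that censors at death and discharge gives a cause-specific hazard ratio, which is a valid quantity. The excess in 1 minus Kaplan-Meier does not carry over to it.
- **Informative discharge is not shown.** It is plausible that patients at higher risk stay longer, but no section says so and the table above does not use it. The gap there is between two quantities: risk by day 21 if everyone stayed, and risk during the actual stay. The first is legitimate, but it is not the endpoint in section 3.5.
- **Symptomatic events are not lost to the trial.** Symptomatic PE and total VTE have their own Fisher comparisons. No symptomatic rate is given, so the effect of how these events are handled in the Cox model cannot be sized.

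**Conclusion.** The point holds for a secondary analysis. The rule is wrong as written because it names the event as a censoring time and leaves symptomatic VTE unassigned. For an endpoint that exists only in hospital, 1 minus Kaplan-Meier with death and discharge censored does not estimate inpatient incidence.

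Under uniform stays of 7 to 21 days, stay unrelated to thrombosis and 30% inpatient incidence, the control-arm excess at day 21 runs from none to about 12 points. It is close to nil if thromboses come early. The documents do not say where in that range this trial lies, so 12 points is not a forecast. The primary Fisher comparison and the sample size are unaffected.

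**What to change.** In section 8, replace the censoring sentence with statements that:

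1. the event is the first asymptomatic lower-limb thrombosis found on DUS, dated at the positive scan;
2. a patient without an event is followed until death or discharge;
3. a symptomatic DVT or PE that comes first is a competing event, and a supportive analysis counts any first VTE as the event.

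Plot Aalen-Johansen cumulative incidence by arm, with death, discharge and earlier symptomatic VTE as competing events, in place of the Kaplan-Meier curves or beside them. If every patient is followed to one of these outcomes, this curve ends at the proportion that the primary analysis reports. Label the Cox results as cause-specific hazard ratios.

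Making any VTE the main event would not be a neutral correction. It would replace the primary endpoint with something close to the secondary endpoint of total VTE, so it belongs in the supportive analysis.

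The cost is SAP wording and slightly more analysis work with a standard routine. The dates of VTE, death and discharge are already needed for the present rule, so no new data are required.

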#### **Inclusion criteria:**

- Age over 40 years;
- Major surgery required;
- High risk of postoperative VTE;
- Caprini score of 11 or more (at extremely high risk of VTE);
- Informed consent is given.

Age over 40 years is suggested as an inclusion criterion by the Russian National Guidelines on VTE prevention, which recognize these patients as a standard high-risk group if undergoing major surgery.

Major surgery is recognized as any procedure under general or regional anesthesia with the leg motor block with a duration of 45 min and more that are equal to major surgery (>45 min) or laparoscopic surgery (>45 min) in the Caprini model.

Primary risk assessment for postoperative VTE should be made according to the rules of the Russian National Guidelines, and only patients at high-risk (major surgery in patients of 40–60 years old with additional individual risk factors, or major surgery in

patients of 60 and more years old independent of additional risk factors) will be screened for eligibility according to the Caprini score.

The Caprini score should be assessed twice: at the baseline screening before inclusion and before discharge or after death. It will be allowed to include patients with supposed scores of  $\geq 11$  (e.g., supposed cancer, supposed long bed rest, supposed CHF, CVD, etc.), but not less than 9. The final assessment of concomitant diseases as risk factors will be performed by an invited specialist. The maximal Caprini score will be taken into account.

**Exclusion criteria:** acute DVT at baseline; performed IVC plication or implanted IVC filter; regular preoperative anticoagulation; postoperative anticoagulation needed at therapeutic doses; absence of anticoagulation  $>5$  days after surgery; coagulopathy (not related to DIC syndrome); thrombocytopenia; hemorrhagic diathesis; lower limb soft-tissue infection; lower limb skin lesion; ankle-brachial index  $<0.6$ .

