#### **4.2. Low-molecular-weight heparins**

Standard doses of 40 mg Enoxaparin (Clexane, Sanofi-Aventis, France) subcutaneously once daily is prespecified. Following Russian National Guidelines, the first injection should be done 12 h before the surgery (elective surgery without high bleeding risk) or within 12 h after surgery (emergent surgery, procedure with high bleeding risk). In the case of the highest bleeding risk, it is allowed to delay the first LMWH injection for 5 days. The patients who did not receive Enoxaparin after 5 days will be withdrawn from the analysis. The pharmacoprophylaxis should be continued until the patient's discharge from the hospital (not less than 7 days) or death. The prolonged prophylaxis with LMWH is not pre-specified and will depend on the surgeon's preference. The enoxaparin administration and the control for injection should be made within the standard clinical practice.

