### **5.2. VTE risk assessment**

The primary VTE risk assessment should be performed by Russian National Guidelines, and if the patient will be classified as having a high risk (major surgery in subjects over 60 years old or major surgery in subjects from 40 to 60 years old having additional individual risk factors for VTE), he should be assessed by Caprini score. A Russian adaptation of the 2005 version of the Caprini score will be used (Fig. 3).

The primary risk assessment will be performed before randomization. Any patients that will receive or will be supposed to receive (e.g., supposed prolonged bed rest in ICU, supposed malignancy, CHF, COPD, bowel inflammatory disease, thrombophilia, etc.) a score of 11 or more, should be invited into the study. The calculation of the final Caprini score should be done before discharge or after patients' death. So, all new condition and complications occurred during the inpatient treatment period will be considered. However, some enrolled patients may decrease their score because of unexpected early ambulation, misdiagnosis of malignant disease or other co-morbidities.

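### The adjusted Cox model does not say which Caprini score it uses; under the only rule given, the score can include events after allocation and bias the hazard ratio

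*Combined protocol and SAP*

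**What the plan says.** The primary analysis in section 8 is "intention-to-treat with the use of two-tailed Fisher's exact test to compare the primary endpoint between two groups". An unadjusted Cox model of the same endpoint follows. Adjusted Cox models then add clinical center, surgery profile, type and urgency of surgery, anesthesia and radicalism, and the list closes with "malignant disorder, Caprini score, and time to start LMWH injections will be used". A similar analysis is planned in the per-protocol population. Section 8 does not say which Caprini score is meant, or how any covariate is coded.

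The text on inclusion criteria (section 3.2) has the score assessed at baseline screening and again before discharge or after death, and adds: "The maximal Caprini score will be taken into account". Section 5.2 places the first assessment before randomization. Of the final score it says that "all new condition and complications occurred during the inpatient treatment period will be considered".

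Section 4.2 sets the first LMWH injection 12 h before surgery or within 12 h after it, according to urgency and bleeding risk. At the highest bleeding risk, "it is allowed to delay the first LMWH injection for 5 days".

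**The concern.** A covariate in a model of a randomized comparison should be fixed before allocation. Otherwise treatment or outcome may have altered it, and the adjusted HR no longer estimates the effect of allocation. More patients do not cure this.

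The final Caprini score is open to that problem. In the Cox model, follow-up ends at VTE, death or discharge. The second score is taken about when follow-up ends, or after it, yet would be entered as if known at the start.

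The documents give plausible routes for the score to change. The form gives 2 points for confinement to bed beyond 72 h, and section 1 notes that IPC devices tend to keep patients in bed. Section 5.2 expects some scores to change with early ambulation. Complications of the stay also count.

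The adjusted HR is a prespecified result for the primary endpoint. Allocation follows a digit of the record number, so readers may turn to the adjusted estimate when they worry about imbalance.

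**Working it through.** **Plan's own figures.** The control rate "was assumed as 30% based on our previous observations involving patients at high and extremely high risk" and "the absolute difference of 18% is assumed", so the IPC rate is 0.30 − 0.18 = 0.12. The design is set "with a power of 80% and type I error of 0.05".
- Uncorrected two-proportion formula: n = [1.96·√(2·0.21·0.79) + 0.842·√(0.30·0.70 + 0.12·0.88)]² / 0.18² = 79.2, so 80 per group.
- With continuity correction: 90 per group. Exact Fisher power at 90 per group is 0.812. The plan's 90 + 90 is reproduced.
- Withdrawal: 180/0.90 = 200. Doubled: 400 enrolled, of whom 0.90 × 400 = 360 remain.

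**Which score enters the model.**

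| Place | What it settles |
|---|---|
| Section 8 | A Caprini score is a covariate; which one is not stated |
| Section 3.2 | Two assessments; the maximum counts |
| Section 5.2 | First assessment before randomization; the final one includes complications of the stay |

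The documents hold no other rule for choosing between the two scores.

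**Size of the Caprini bias if the maximum is used.** The true HR implied by the design is ln(0.88)/ln(0.70) = 0.358. The simulation had 360 patients, 14 days of follow-up and 17 parameters. Covariate frequencies, a Caprini slope of 0.15 log-hazard per point, and a score rise in half of the patients with an event were assumed. There were 300 runs per row.

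| Rise | Median HR, screening score | Median HR, maximal score |
|---|---|---|
| 2 points | 0.348 | 0.360 |
| 3 points | 0.351 | 0.387 |

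For 3 points the shift in log-HR is ln(0.387/0.351) = 0.098, about a third of its standard deviation across runs (0.288 to 0.300). It is towards no effect.

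The opposite direction is possible. Suppose IPC has no effect, but an extra 20–40% of IPC patients gain 2 points for bed confinement. With 40% of controls assumed confined, the adjusted HR is 0.98–0.93 at 0.1 log-hazard per point and 0.91–0.88 at 0.3. Another simulation of this scenario, whose slope is not recorded, gave 0.90–0.83.

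**Number of parameters.** With the levels listed in sections 5.4 and 8: treatment 1 + center 1 + profile 4 + type 2 + urgency 2 + anesthesia 2 + radicalism 1 + malignancy 1 + Caprini 1 + LMWH start 2 = 17. It is 16 if LMWH start is continuous, and more if profile has over five levels.

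Expected events:
- 360 patients, 1:1: 180 × 0.30 + 180 × 0.12 = 75.6, or 75.6/17 = 4.4 per parameter.
- All 400, 1:1: 200 × 0.30 + 200 × 0.12 = 84, or 4.9 per parameter.
- All 400 under the digit rule: a final zero passes to the previous digit, so four of the nine usable digits lead to IPC. 400 × (5/9 × 0.30 + 4/9 × 0.12) = 88, or 5.2 per parameter.

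In 600 runs with about 75 events, 17 parameters and the screening score, the standard deviation of the treatment log-HR was 0.282, against 0.267 unadjusted (0.282/0.267 = 1.06). Coverage of the 95% interval was 94.5% against 94.7%. About 2% of runs had a very large coefficient, consistent with a sparse category.

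**The case against.** The strongest reply is that section 8 never names the maximal score. The sentence on the maximum stands among the inclusion criteria, next to the allowance for supposed scores, and may have been meant only to settle who counts as extremely high risk. This stands in part: a reader might infer that the plan definitely adjusts for the maximal score, and the text does not establish that. What remains is a plan that leaves the choice open while its only stated rule points to the unsuitable option.

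The simulated HRs rest on invented inputs. No section says that the index thrombosis earns the 3 points for DVT/PE history. Swollen legs fit poorly as a consequence of an asymptomatic endpoint. Expected bed rest may already be scored at screening. All of this stands, so the figures show that bias is possible in either direction; they do not predict it.

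LMWH start is not later than allocation in every patient. The first dose may precede elective surgery, and emergency patients may be enrolled up to 12 h after the operation, when it may already have been given. Longer delay is reserved for the highest bleeding risk. No documented route leads from IPC to LMWH timing, and no simulation covers it. This also stands. The weaker concern is that, in an open-label trial, staff who can know the arm decide the timing over a window that extends to 5 days.

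A reader might also infer from 4 to 5 events per parameter that the treatment HR is unstable. The simulation does not support that: its spread rose by about 6% and coverage held.

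**Conclusion.** The point holds as a gap in specification with a real risk of bias. The plan does not fix the Caprini covariate before allocation, and its only rule on which score counts would admit in-hospital events. Adjusting for such a score can move the treatment HR either way. Under the assumed 3-point rise in half of the patients with an event, the move is from 0.351 to 0.387; the true amount cannot be known from the documents. Actual LMWH start is a lesser instance, without a quantified effect.

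The point should not be read as undermining the primary result: the Fisher test and the unadjusted Cox model use neither covariate. Nor is it a case for a particular short covariate list. About 17 parameters for 76 to 88 events mainly makes the coefficients of sparse categories unreliable, and that count itself depends on coding the plan leaves open.

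**What to change.** In section 8, state that the Caprini covariate is the score recorded at screening, before allocation, in both the intention-to-treat and per-protocol Cox models. Because section 3.2 admits patients on supposed scores, say also whether points for supposed conditions are included. The final or maximal score can still be reported descriptively.

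Remove actual time to LMWH start from the main adjusted model, or replace it with the timing planned before allocation. A model with actual start time can be kept as a labelled sensitivity analysis. State the coding of each covariate, and do not interpret coefficients from sparse categories.

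Naming the score and removing LMWH start cost only SAP wording, since the screening score is already collected. Using planned LMWH timing would also require that plan to be on record before allocation; the documents do not list it as a data item.

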### **3.3. Patient's withdrawal from the study**

Patient's withdrawal from the study will be possible in case of the patient's refusal from further participation, the occurrence of serious adverse events necessitating early termination of study procedures, as well as meeting the criteria for patient's withdrawal from the study. The criteria for withdrawal are as follows: the occurrence of any VTE event, considered as a primary or secondary endpoint; the occurrence of major or non-major clinically relevant bleeding, considered as secondary endpoints, required the discontinuation of LMWH administration; the occurrence of leg skin injury, considered as a secondary endpoint; required discontinuation of IPC application; the occurrence of any clinical condition required discontinuation of IPC or ECS application (e.g., leg ischemia, compartment syndrome); the occurrence of any clinical condition that required discontinuation of LMWH administration (e.g., thrombocytopenia, allergic reaction); the occurrence of any clinical condition that required changes in the VTE prophylaxis modality (e.g., change in dose and type of anticoagulation); and the occurrence of any exclusion criteria after randomization.

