#### **5.4. Examination during inpatient treatment**

The following data on surgical procedure should be obtained from the medical records after intervention: the surgical profile (e.g., abdominal, thoracic, neck, pelvis, cranial), type of surgery (open, endoscopic, endoscopy assisted), urgency of surgery (emergent = performed in 0–2 h after admission, urgent = performed in 0–6 days after admission, elective = performed independently at the time of admission), radicalism of surgery (radical, palliative), type of anesthesia (general, regional, combined), surgery duration, blood loss, and intraoperative infusion.

The routine clinical examination of the patient will be performed in a daily manner with special attention to the possible complications, such as DVT, SVT, PE, bleeding, and leg skin injury. IPC sleeves should be removed for 15–20 mins every day for skin inspection and investigation of pedal pulsation. Consultation of any relevant specialist

(cardiologist, neurologist, pulmonologist, infections) should be performed if any complication or development of new co-morbidity will be observed during the follow-up.

DUS should be performed every 3–5 days after surgery and in emergency manner if any clinical suspicion for DVT or SVT appeared. In an emergency manner, DUS may be performed by a blinded expert or specialist on duty on weekend and holidays. However, all conclusions of non-investigational medical staff must be verified by a blinded expert.

SPECT/CT or CTPA should be used to verify PE in an emergency manner if clinical suspicion appeared. An autopsy must be performed in all died patients to verify the absence of DVT and PE.

In case of any clinical suspicion for a VTE event, IPC should be interrupted until final verification of the diagnosis. In the case of positive DUS, CTPA, and SPECT/CT, the therapeutic anticoagulation should be prescribed, and IPC should be removed. In the case of clinical suspicion for VTE with negative results of instrumental tests, IPC should not be returned until the proper diagnosis that mimics VTE will be found.

Any revealed leg skin lesion should be judged individually for the possibility to continue ECS and IPC application. If the decision will be made to stop IPC, the patient should be withdrawn from the study according to the protocol.

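### Read literally, the per-protocol rule excludes IPC patients because they reached the primary endpoint, and it leaves open whether control-arm events are excluded too

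*Combined protocol and SAP*

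**What the plan says.** The primary endpoint (section 3.5) is "asymptomatic venous thrombosis of the lower limbs detected by DUS during inpatient treatment". Section 8 analyses it by intention to treat with a two-tailed Fisher's exact test. It then plans a similar analysis in a per-protocol population and names per-protocol again among the sensitivity analyses. That population leaves out patients with gross protocol violations and those with "premature discontinuation of at least one component of combined prophylaxis (ECS, IPC or LMWH". The word premature is not defined, and nothing is said about the timing of the stop or the reason for it.

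Four other sections bear on who stops a component:

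- Section 4.3 requires IPC throughout the hospital stay.
- Section 4.2 plans enoxaparin at a prophylactic dose, in both arms, until discharge or death.
- Section 5.4: "In the case of positive DUS, CTPA, and SPECT/CT, the therapeutic anticoagulation should be prescribed, and IPC should be removed". On clinical suspicion alone, "IPC should be interrupted until final verification of the diagnosis"; if the tests are then negative, "IPC should not be returned until the proper diagnosis that mimics VTE will be found".
- Section 3.3 lists as a reason for withdrawal, in either arm, "the occurrence of any VTE event, considered as a primary or secondary endpoint". It also lists, as separate items, conditions that require LMWH to be stopped and conditions that require the prophylaxis to be altered, giving a different anticoagulant dose or type as the example.

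**The concern.** A per-protocol set is meant to select on adherence. Here, one way of becoming non-adherent is to have the outcome. An IPC patient whose scan shows thrombosis has IPC taken off under the protocol before its planned end, so the exclusion follows from the endpoint itself. Control patients have no IPC to remove, so whether they are excluded depends on a different question: whether replacing prophylactic LMWH with therapeutic anticoagulation counts as discontinuing LMWH.

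What is at stake is the analysis that readers will use to check the intention-to-treat result. If exclusion depends on the event in one arm only, it can show a benefit where there is none, or enlarge a real one. If it depends on the event in both arms, no events are left to compare.

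**Working it through.** **Inputs.** From section 8: control rate 30%; 60% relative reduction, so an 18-point difference and 12% under IPC; 80% power; type I error 0.05; 90 per arm; 10% withdrawal; sample size then doubled.

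**The plan's own figure.** The usual two-proportion formula, with mean proportion 0.21, gives

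n = [1.96·√(2·0.21·0.79) + 0.842·√(0.30·0.70 + 0.12·0.88)]² / 0.18² ≈ 79.2, or 80 per arm.

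With the continuity correction, n' = (n/4)·[1 + √(1 + 4/(n·0.18))]² ≈ 90 per arm, which matches the plan. Exact enumeration of the two-sided Fisher test at 90 per arm gives power 0.812. Then 180/(1 − 0.10) = 200, and doubling gives 400, taken here as 200 per arm.

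**Expected events.** Control: 200 × 0.30 = 60. IPC at the planning rate: 200 × 0.12 = 24. IPC with no true effect (an assumption used as a test case): 200 × 0.30 = 60.

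**Applying the exclusion.** An excluded event leaves both the numerator and the denominator. If all IPC-arm events go, 24 of 200 becomes 0/(200 − 24) = 0/176; with no effect, 60 of 200 becomes 0/(200 − 60) = 0/140. If all control events go, 60 of 200 becomes 0/140. The share of events excluded is not given in the documents, so a range is shown, in part because the rule might not be applied to every event.

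| Share of events excluded (IPC / control) | Planning rates, IPC vs control | No true effect, IPC vs control |
|---|---|---|
| none / none | 24/200 vs 60/200, RR 0.40 | 60/200 vs 60/200, RR 1.00 |
| quarter / none | 18/194 vs 60/200, RR 0.31 | 45/185 vs 60/200, RR 0.81, p = 0.25 |
| half / none | 12/188 vs 60/200, RR 0.21 | 30/170 vs 60/200, RR 0.59, p = 0.007 |
| all / none | 0/176 vs 60/200, RR 0 | 0/140 vs 60/200, RR 0, p ≈ 3 × 10⁻¹⁶ |
| half / half | 12/188 vs 30/170, RR 0.36 | 30/170 vs 30/170, RR 1.00 |
| all / all | 0/176 vs 0/140, RR not estimable | 0/140 vs 0/140, RR not estimable |

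The p-values are two-sided Fisher tests on the expected counts. The all / none row is the literal rule if the anticoagulant change does not count as stopping LMWH. The all / all row is the literal rule if it does. The first row is what remains when endpoint-driven stops are ignored and nobody is excluded for another reason.

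**The case against.** **Premature can be read harmlessly.** Section 8 ends each patient's time in the Cox model at VTE, death or discharge, and section 3.3 ends participation at an endpoint VTE. On that view, removing IPC after a positive scan happens once the observation is complete and is not premature. This may well be what was intended, since a per-protocol analysis without endpoint cases makes no sense. But it is nowhere stated. The Cox time rule does not define who belongs to the per-protocol set. The trial is also open-label with the allocation list held by the investigator (sections 3 and 3.1), so an undefined term leaves exclusions to judgement when arm and outcome may both be known.

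**The loss need not be one-sided.** A reader might infer that only IPC-arm events disappear because controls merely have their LMWH increased. No section says that. The instruction in section 5.4 to start therapeutic anticoagulation names no drug and is not limited to one arm. Section 4.2 describes the LMWH component at a prophylactic dose. Sections 3.2 and 3.3 together make a need for therapeutic-dose anticoagulation a reason for withdrawal. On the other side, section 3.3 lists stopping LMWH apart from a change of dose or type, which favours the one-sided reading without settling it. This objection stands: the asymmetry is possible, not established.

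**Two further arguments add little.** Interruption on suspicion is a minor route, because the endpoint is asymptomatic; where tests are negative it removes IPC patients without events, which slightly raises the IPC rate. That IPC patients can stop three components and controls two is inherent in an add-on design.

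**Conclusion.** The per-protocol rule is defective as written. Taken literally, it excludes every IPC patient who reaches the primary endpoint before discharge. What happens to control patients with the same event depends on a question the documents leave open. At 200 per arm and the planning rates, the result is either 0/176 against 60/200, which exaggerates a true benefit (and at 0/140 against 60/200 invents one where there is none), or 0/176 against 0/140, which gives no relative risk. Neither can serve as a check on the main analysis. Partial application matters too: with no true effect, losing half of the IPC-arm events alone gives a relative risk of 0.59.

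These figures rest on equal arms of 200, the section 8 rates, and no exclusions for other reasons.

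Two stronger conclusions are not supported. One is that the trial's main result is biased: the primary analysis is by intention to treat and does not use this rule. The other is that the per-protocol result will confirm IPC whatever its effect: that requires the one-sided reading and near-literal application, and a complete absence of IPC-arm events would look suspect beside the intention-to-treat result.

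**What to change.** Add to section 8 that per-protocol status is judged, by the same rule in both arms, only on the time before the first confirmed VTE, death or discharge. Add also that stopping, interrupting or changing a component because VTE is suspected or confirmed, including the switch to therapeutic anticoagulation, does not count as premature discontinuation. Reconcile sections 3.3, 5.4 and 8 so that withdrawal at an endpoint VTE is not taken as a reason for per-protocol exclusion.

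The cost is one or two sentences and a cross-reference. No clinical instruction changes. The analyst needs the date and reason of each stop. The daily compliance sheet in section 5.6 should help to date IPC stops; that section provides no specific measure for stockings or LMWH, so those stops would have to come from routine records.

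Censoring patients in the Cox model when they stop a component for a reason other than VTE is not part of this recommendation, because it brings its own informative-censoring problem.
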